			Section 7.1.1 updated to reflect that the category with the highest number of inhalations will be reported if there is a tie in the most frequent usage.	Clarification
			Section 7.5.2 updated with modified analyses.	For this exploratory study, analyses methods were updated in the spirit of the protocol to better address study objectives and to align with the ancillary analytics report.
			Section 7.5.2.4 updated.	Clarification
			Section 7.5.3 updated to clarify that the analyses will be done by the data analytics group.	Clarification
			Section 10.4 updated to clarify the definition of treatment emergent.	Clarification

LIST OF ABBREVIATIONS AND DEFINITIONS OF TERMS

Abbreviation	Term
ABS	albuterol sulfate
BMI	body mass index
CE-COPD	clinical exacerbation of COPD
CI	confidence interval
COPD	chronic obstructive pulmonary disease
CSR	clinical study report
CTCAE	Common Terminology Criteria for Adverse Events
D _{emdpi}	eMDPI time on study
eCRF	electronic case report form
EDC	electronic data capture
eMDPI	multidose dry powder inhaler with an eModule
FEV ₁	forced expiratory volume in 1 second
GCP	Good Clinical Practice
ICF	informed consent form
ICS	inhaled corticosteroid
IMP	investigational medicinal product
IRB	Institutional Review Board
ITT	Intent-to-Treat
LABA	long-acting beta agonist
LAMA	Long-acting muscarinic antagonist
MDI	metered dose inhaler
MDPI	multidose dry powder inhaler
MedDRA	Medical Dictionary for Regulatory Activities
MIF	maximal inhalational flow
mITT	Modified Intent-to-Treat
PP	Per-Protocol
R&D	Research and Development
SABA	short-acting beta ₂ agonist
SAMA	short-acting muscarinic antagonist
SCS	systemic corticosteroid
SD	standard deviation

Abbreviation	Term
SDI	sleep disruption index
SE	standard error
TDS	total daily steps
SOC	system organ class
SOP	standard operating procedure
WHO	World Health Organization

INTRODUCTION

This Statistical Analysis Plan describes the planned analysis and reporting for Teva Branded Pharmaceutical Products R&D, Inc. Study ABS-COPD-30065 (A 12-Week, Open-Label Study to Evaluate the Relationship Between Use of Albuterol eMDPI, an Inhaled Short-Acting Beta Agonist “Rescue” Agent with an eModule, and Exacerbations in Patients (40 Years of Age or Older) with Chronic Obstructive Pulmonary Disease), and was written in accordance with standard operating procedure (SOP) GBP_RD_702 (Statistical Analysis Plan).

The reader of this Statistical Analysis Plan is encouraged to read the study protocol for details on the conduct of this study, the operational aspects of clinical assessments, and the timing for completing the participation of a patient in this study. The Statistical Analysis Plan is intended to be in agreement with the protocol. However, the Statistical Analysis Plan may contain more details regarding these particular points of interest, or other types of analyses (eg, other endpoints). When differences exist in descriptions or explanations provided in the study protocol and this document, the Statistical Analysis Plan prevails; the differences will be explained in the clinical study report (CSR) or in this document.

1. STUDY OBJECTIVES AND ENDPOINTS

1.1. Objectives and Endpoints

The objectives of this study are to explore the pattern and amount of albuterol use (as captured in the albuterol sulfate (ABS) multidose dry powder inhaler with an eModule (eMDPI), alone or in combination with other study data, preceding a moderate or severe CE-COPD (as diagnosed by the investigators per the protocol). The hypothesis is that albuterol use will increase several days prior to a moderate or severe CE-COPD and can serve as a marker of COPD deterioration.

The endpoints of the trial are the primary outcome measure (ie, CE-COPD) and the primary outcome predictor (ie, albuterol use) alone or in combination with secondary predictors (ie, other study data). These predictors of CE-COPD will be modeled to determine which patterns best predict the subsequent development of CE-COPD.

For albuterol use, parameters of interest will include (1) the total number of inhalations in the days preceding the peak of a CE-COPD, (2) the number of days prior to the peak of a CE-COPD when albuterol use increased, and (3) the number of albuterol uses in the 24 hours preceding a CE-COPD. Therefore, endpoints are not designated as either primary or secondary.

In addition to albuterol use, inspiratory flow values (maximal inhalational flow (MIF), inhalational volume, inhalation duration, and time to MIF), sleep disruption index (SDI), total daily steps (TDS), and baseline information regarding disease state and demographics will be studied. These data will be analyzed using both a univariate and multivariate approach, to determine which patterns best predict the subsequent development of a CE-COPD. Inspiratory flow values are obtained from the eMDPI, SDI is obtained for a subset of patients who agree to participate at specific investigational centers (n=100) from an accelerometer worn on the wrist, and TDS is obtained for a subset of patients who agree to participate at specific investigational centers (n=100) from an accelerometer worn on the ankle. Baseline disease state and demographic information will be obtained at screening.

Another objective for this study is to evaluate the safety of ABS eMDPI use in patients with exacerbation-prone COPD.

The safety endpoints for this study include the following:

- adverse event data
- physical examinations

2. STUDY DESIGN

2.1. General Design

This is a 12-week, multicenter, open-label study to evaluate the relationship between as-needed usage of ABS eMDPI and CE-COPD in adult patients at least 40 years of age with exacerbation-prone COPD. ABS eMDPI is a rescue/reliever agent that includes an eModule on top of the approved PROAIR® RESPICLICK inhaler. The on-board electronics and power source are fully integrated into the inhaler and are designed to operate for the life of the inhaler without intervention. The electronic module records timestamped, pre-defined events such as cap open and inhalation parameters. The inclusion of the eModule has been shown to have no impact on the dose delivery compared with the approved product without the eModule.

The study will consist of a screening period of up to 2 weeks and a 12-week intervention period.

After providing written informed consent, patients will complete a screening visit (visit 1) to determine eligibility for the study. Patients will provide medical history (including prior medications), complete a physical examination, pregnancy test, if applicable, and review COPD exacerbation history. Eligible patients will return to the investigational center within 2 weeks for the baseline visit (visit 2). Those meeting entry criteria will be trained on the use of the eMDPI device and, upon demonstrated competency, will receive ABS eMDPI devices for use as rescue bronchodilators during the study. The screening visit and baseline visit may be combined.

Patients must use ABS eMDPI as their only rescue agent for the duration of their participation in this study and will be advised to place any current rescue pills, inhalers, or nebulizers, including SABA, short-acting muscarinic antagonists (SAMAs), or SABA/SAMA combination into storage. Patients may continue the use of other COPD and non-COPD medications as advised by their physician without changes unless deemed necessary by their physician. Patients will be managed according to routine clinical practice by their treating physician with no specific study-related instructions provided other than those on the proper use of ABS eMDPI.

Patients will be contacted by phone on a monthly basis for the collection of information about COPD exacerbations and treatments, concomitant medications, and adverse events. A review of the instructions for the use of ABS eMDPI and the procedure for replacement and return of ABS eMDPI will also occur during the monthly call.

Patients will receive initial eMDPI devices at visit 2 based on anticipated usage pattern. In the event that additional eMDPI devices are needed, patients will be required to visit the investigational center to receive them. Patients will be instructed to return all inhalers to the investigational center at the last study visit or earlier, including at the early termination visit, as well as at any other point if there is a problem with the inhaler. At the last study visit or early termination, patients will be queried for adverse events, concomitant medications, and COPD exacerbations; a physical examination will be completed; and the patient will subsequently be discharged from the trial.

Two subsets of patients who agree to participate at specific investigational centers and wear an accelerometer either on the ankle to measure TDS (n=100) or on the wrist to measure SDI (n=100) will be instructed on the proper use of these devices at the baseline visit (visit 2). The

devices will be worn throughout the 12-week intervention period and will be returned to the investigational center at the final visit or upon early termination (visit 5).

The end of study is defined as the last visit of the last patient.

The study duration will be approximately 9 months.

Study procedures and assessments with their timing are summarized in [Table 1](#) of the study protocol.

Table 1: Study Procedures and Assessments

Study period	Pre-intervention		Intervention				
	V1	V2	V3 ^a	V4 ^a	Vz	V5	
Visit number	Day -14 to Day 1	Day 1	Day 28 ±7 days	Day 56 ± 7 days	Up to 14 days after CE-COPD start date	Day 84 ±14 days	
Procedures and assessments	Screening	Baseline	Phone visit	Phone visit	Exacerbation visit	Final/early termination visit	
Informed consent	X						
Inclusion and exclusion criteria	X	X					
Assign patient number	X						
Medical history	X						
Prior medication and treatment history	X						
Physical examination, including height and weight ^b	X				X	X	
Vital signs measurement ^c	X						
Urine pregnancy test for women of childbearing potential	X						X
Inform patients of study compliance for eMDPI and accelerometer and requirement for provider visit in the event of CE-COPD	X	X	X	X			
Assess for COPD exacerbations	X	X	X	X			X
Adverse events inquiry		X	X	X	X		X
Wearable accelerometers: dispense, training, and collection ^d		X					X
ABS eMDPI: dispense, training, collection, and accountability ^e		X			X		X
Concomitant medication inquiry	X	X	X	X	X		X

^a Investigational centers must obtain source documentation for all COPD exacerbations that occur during the treatment period to confirm the accuracy of the information obtained from the patient.

^b Height will be measured at the screening visit only.

^c Vital signs measurements will include blood pressure, respiratory rate, and heart rate.

^d Wearable accelerometers for a subset of patients who agree to participate at specific investigational centers will be dispensed at visit 2, and SDI and TDS data will be collected continuously from visit 2 through visit 5 via the wearable accelerometer. Instructions for proper use of the devices will be provided to patients at visit 2. The devices will be collected at visit 5.

^c Patients will receive initial eMDPI devices at visit 2 based on anticipated usage pattern. In the event that additional eMDPI devices are needed, patients will be required to visit the investigational center to receive them. Patients will be instructed to return all inhalers to the investigational center at the last study visit or earlier, including at the early termination visit, as well as at any other point if there is a problem with the inhaler. Instructions for dispensing, proper clinical use, and collecting ABS eMDPI will be provided to patients at visit 2 and reviewed during the monthly calls.

ABS = albuterol sulfate; CE-COPD = clinical exacerbation of chronic obstructive pulmonary disease; COPD= chronic obstructive pulmonary disease; eMDPI=multidose dry powder inhaler with an eModule; SDI = sleep disruption index; TDS=total daily step; V = visit.

Note: Screening and baseline visits may be combined.

2.1.1. Treatment

2.1.1.1. Investigational Medicinal Products Used in the Study

Patients will receive initial eMDPI devices at visit 2 based on anticipated usage pattern and return all inhalers to the investigational center at the last study visit or earlier, including at the early termination visit (visit 5), as well as at any other point if there is a problem with the inhaler.

2.1.1.2. Test Investigational Medicinal Product

ABS eMDPI is an inhalation-driven MDPI containing a blend of ABS and alpha-lactose monohydrate. The inhaler contains 200 actuations, each delivering 90 mcg of albuterol base ex-mouthpiece; the inhaler is equipped with a dose counter that shows only even numbers and counts down to “0”.

Additional details may be found in Table 2 of the protocol.

2.1.1.3. Starting Dose and Dose Levels

The prescribed dose will be 90 mcg, 1 to 2 inhalations every 4 hours as needed. No dose escalations are planned.

2.2. Randomization and Blinding

This is a nonrandomized study. All patients will use the 1 Test investigational medicinal product (IMP), the ABS eMDPI. Blinding is not applicable.

2.3. Sample Size and Power Considerations

Assuming an expected dropout rate of 10%, it is recommended that 400 patients be enrolled so that 360 evaluable patients complete the study. These conclusions are based on a review of the relevant literature, as follows.

Based on previous studies of an exacerbation-prone COPD cohort ([Dransfield et al 2013](#), [Vogelmeier et al 2011](#), [Wedzicha et al 2013](#), [Wedzicha et al 2016](#)), it is expected that 91 (range, 73 to 110) CE-COPD events will occur over the 12-week evaluation period in this study based on reported CE-COPD exacerbation rates of 1.05 and 1.14 events per year. Furthermore, it is expected that 14% (14) of total exacerbations will be severe.

This sample size (ie, n=400 patients, 73 to 110 CE-COPD events) is considered adequate for the fulfillment of the study objectives to evaluate the relationship of albuterol use, inspiratory flow, SDI, and TDS data associated with a subsequent CE-COPD event. Per a previous study ([Jenkins et al 2013](#)), a statistically significant relationship was established between daily SABA usage and subsequent CE-COPD.

In the present study, approximately 73 to 110 CE-COPD events are desired because the model's fitting of the current study involves the analysis of multiple predictors as described in more detail below. Because the largest model considered has 7 covariates, it is desirable to have at least 70 events. The probability to observe at least 70 CE-COPD events is higher than 0.99.

Risk models published in the literature have typically included between 4 and 6 covariates/risk factors ([Bateman et al 2015](#), [Greenberg et al 2012](#), [Quezada et al 2016](#)) to examine the relationship between possible risk factors and a disease. When there is more than 1 covariate (risk factor) in the model, multiple logistic regression may be used to estimate the relationship of a specific covariate of interest (ie, albuterol use) to a primary outcome (ie, CE-COPD), adjusting for the other/remaining covariates (risk factors). In this case, the required sample size to estimate such a relationship is greater than that for univariate logistic regression.

The number of events per variable has been suggested as a criterion for the size of a data set ([Harrell et al 1984](#), [Laupacis et al 1997](#), [Peduzzi et al 1996](#),). The rule of thumb when building logistic regression models is 1 predictor variable for every 10 events ([Peduzzi et al 1996](#), [Vittinghoff and McCulloch 2007](#)). Therefore, this sample size would be adequate for predicting the primary outcome (CE-COPD) using multiple logistic regression, including the covariate of primary interest (ie, albuterol use) and the remaining multiple predictors (inspiratory flow values, SDI, and TDS) as potential risk factors for CE-COPD in the model for this patient population.

2.4. Sequence of Planned Analyses

2.4.1. Planned Interim Analyses

There will be no formal interim analysis for this study.

2.4.2. Final Analyses and Reporting

All analyses identified in this Statistical Analysis Plan will be performed after the end of the study as defined in the study protocol.

Data used for final statistical analyses will be derived from various sources including eCRF, data from ABS eMDPI inhaler, wrist, and ankle accelerometers.

This Statistical Analysis Plan and any corresponding amendments will be approved before database lock, in accordance with SOP GBP_RD_702 (Statistical Analysis Plan).

3. ANALYSIS SETS

3.1. Intent to Treat Analysis Set

The intent-to-treat (ITT) analysis set will include all enrolled patients regardless of whether a patient took any IMP. A patient is considered enrolled according to the status reported in the database. This analysis set will be used for endpoint analysis and safety analysis.

3.2. Modified Intent-to-Treat Analysis Set

The modified intent-to-treat (mITT) analysis set is a subset of the ITT analysis set that will include patients who used the IMP at any time during the study and patients who did not use the IMP at any time during the study provided these patients complied with study requirements and the data from the ABS eMDPI inhalers were successfully downloaded at the end of the study.

3.3. Safety Analysis Set

The safety analysis set will include all enrolled patients who received at least 1 dose of the IMP.

3.4. Wrist Accelerometry Analysis Set

The wrist accelerometry analysis set is a subset of the mITT analysis set that will include patients who wore a wrist accelerometer with sufficient memory to capture 12 weeks of data during study participation and for whom data from the wrist accelerometer were successfully downloaded at the end of the study.

3.5. Ankle Accelerometry Analysis Set

The ankle accelerometry analysis set is a subset of the mITT analysis set that will include patients who wore an ankle accelerometer with sufficient memory to capture 12 weeks of data during study participation and for whom data from the ankle accelerometer were successfully downloaded at the end of the study.

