4.2.4. Total Daily Steps

Baseline TDS is the average number of daily steps a patient completes, computed using the daily steps recorded during the first 7 days of study participation (study day 1 through study day 7). The average will be calculated as the sum of the daily TDS divided by the number of days with nonmissing TDS. If no step data are available for study day 1 through study day 7, the ‘baseline TDS’ is the first available TDS after study day 7.

Baseline TDS are computed for those patients in the ankle accelerometry analysis set.

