4.6. Handling Withdrawals and Missing Data

Any data that was collected prior a patient's withdrawal from the study will be used for analysis and presented in the data listings.

The following imputation rules will be used;

- If the return date of the last ABS eMDPI device returned is missing the patient's last date of contact if the patient withdrew from the study or the patient's study completion date will be used as the return date (see Section 4.4 and Section 10.2).
- Adverse events or serious adverse events with missing start dates will be considered treatment emergent (see Section 10.4).
- If a patient never used the ABS eMDPI during the study or download of a given ABS eMDPI device was not successful, study day and weekly inhalational flow values will be missing. If download of a given wrist or ankle accelerometer was not successful, TDS and SDI indices will be missing. These missing data will not be imputed.
- In the derivation of Study Day X Inhalation flow values, if there was no albuterol use on Study Day X , then the closest preceding nonmissing Study Day Inhalation is used as the 'Study Day X Inhalation' and the inhalational flow values for Study Day X are assigned accordingly (see Section 7.2.1).
- For patients in the ankle accelerometry analysis set, if no step data are available for study day 1 through study day 7, the 'baseline TDS' is the first available TDS after study day 7 (see Section 4.2.4).
- For patients in the wrist accelerometry analysis set, if no sleep parameter data are available for study day 1 through study day 7, the 'baseline value of a given sleep parameter' is the first available valid sleep parameter value after study day 7 (see Section 4.2.5).
- In the derivation of Study Day X TDS if TDS are missing on Study Day X , then the average of the nonmissing TDS of the 7 days preceding Study Day X is computed and assigned to Study Day X TDS (see Section 7.3.1).
- In the derivation of Study Day X nighttime average sleep latency time if nighttime average sleep latency time is missing on Study Day X , then the average of the nonmissing nighttime average sleep latency time of the 7 days preceding Study Day X is computed and assigned to Study Day X (see Section 7.4.1).

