7.3. Accelerometry: Total Daily Steps

7.3.1. Total Daily Steps Definition

Study Day X and Week Y TDS are defined as follows:

Study Day X TDS: The TDS for study day X are the TDS recorded by accelerometry on study day X . If TDS are missing on Study Day X , then the average TDS of the 7 days preceding study day X is computed and assigned to Study Day X .

Week Y TDS: The TDS for Week Y are computed using the set of TDS taken by the patient during a given week on study. The average will be calculated as the sum of the daily TDS divided by the number of days with nonmissing TDS.

The TDS are computed for those patients in the ankle accelerometry analysis set.

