7.3.2. Analysis Methods for Total Daily Steps

7.3.2.1. Actual and Change from Baseline in Study Day X Total Daily Steps Prior to the Peak of a CE-COPD

Among patients in the ankle accelerometry cohort who experienced a CE-COPD, summary descriptive statistics of the actual TDS and change from baseline in TDS 1 day (eg, the 24-hour period on the day prior to the date of the CE-COPD symptom peak) and at 3, 5, 7, 10, 14, and 21 days preceding the peak of a CE-COPD, will be presented for all CE-COPDs and by moderate CE-COPDs and severe CE-COPDs.

In this analysis, among patients experiencing more than 1 CE-COPD, the subsequent CE-COPDs will be considered a separate CE-COPD distinct from the first (preceding) CE-COPD provided the patient exhibited at least 1 day of baseline albuterol use after the first (preceding) CE-COPD's date of symptom peak and prior to the subsequent CE-COPD's date of symptom peak. For patients who experience multiple CE-COPDs (eg, 3), for a given number of days preceding a CE-COPD (eg, 7 days), if the (eg, third) CE-COPD overlaps with the time period of the preceding (eg, second) CE-COPD, the CE-COPD (eg, third CE-COPD) will not be included in the analysis.

Among patients in the ankle accelerometry cohort, summary descriptive statistics of the actual TDS and change from baseline in TDS, will be presented for overall, by CE-COPD status, by CE-COPD severity (Yes: severe, moderate; No) and for the first occurrence of a single day increase of 20% from baseline use. For patients who experienced a CE-COPD, the single day increase of 20% from baseline use is defined as the single day increase of 20% from baseline use prior to the exacerbation.

In addition, summary descriptive statistics of the maximum change from baseline in TDS will be presented overall and by CE-COPD status and by CE-COPD severity. For patients who experienced a CE-COPD, the maximum change from baseline in TDS is the maximum change from baseline in TDS during the days prior to the exacerbation.

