Week Y Total Time Awake at Night: The total time awake at night for Week Y is computed using the set of total time awake at night times recorded by wrist accelerometry during a given week on study. The average will be calculated as the sum of the total time awake at night times divided by the number of days with nonmissing total time awake at night times.

Study Day X SDI Composite Score: The SDI composite score for study day X is sum of nighttime average sleep latency time, longest nighttime wake episode and total time awake at night on study day X .

Week Y SDI Composite Score: The SDI composite score for Week Y is the sum of nighttime average sleep latency time, longest nighttime wake episode and total time awake at night for Week Y .

The SDIs are computed for those patients in the wrist accelerometry analysis set.

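### The wrist and ankle accelerometry sets are defined by device memory rather than by days recorded, so usable data from before an exacerbation can be left out of the descriptive tables

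*SAP*

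**What the plan says.** **Entry to the sets.** SAP 3.5 admits "patients who wore an ankle accelerometer with sufficient memory to capture 12 weeks of data during study participation", provided the download succeeded. SAP 3.4 uses the parallel condition for the wrist: "patients who wore a wrist accelerometer with sufficient memory to capture 12 weeks of data during study participation". Neither section makes an exception for a partial recording. SAP 20, which lists departures from the protocol, gives no reason for the memory condition.

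**Effect of being outside a set.** SAP 7.3.1: "The TDS are computed for those patients in the ankle accelerometry analysis set". SAP 7.4.1: "The SDIs are computed for those patients in the wrist accelerometry analysis set". Baselines follow the same rule. SAP 4.2.4 says "Baseline TDS are computed for those patients in the ankle accelerometry analysis set", and SAP 4.2.5 restricts the sleep baselines to the wrist set.

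**What the tables use.** Baseline is taken from study days 1 to 7 (SAP 4.2.4, 4.2.5). The TDS pre-peak table reports the day before the peak "and at 3, 5, 7, 10, 14, and 21 days preceding the peak of a CE-COPD, will be presented" (SAP 7.3.2.1), and SAP 7.4.2.1 uses the same time points for sleep. The weekly tables (SAP 7.3.2.2, 7.4.2.2) summarise each study week separately. SAP 7.3.2.1 and 7.4.2.1 also ask for the maximum change from baseline.

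**Partial data elsewhere.** SAP 4.6: "Any data that was collected prior a patient's withdrawal from the study will be used for analysis". It also replaces a missing baseline week with the first later value and fills missing days from the preceding 7 days.

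**The concern.** Memory capacity is a property of the device. Whether a patient can contribute to a table depends on whether the required days were recorded, and the two can differ.

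Take two patients with the same 42 recorded days. One wore a 12-week device and withdrew on Day 42. That patient is in the set, and the data are used under SAP 4.6. The other wore a device that stopped at 42 days and stayed in the study. That patient has no TDS or SDI value in any table, even if a baseline week and the run-up to an exacerbation were captured.

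Each accelerometer subset is planned at 100 patients and is the study's only source of its measure. At stake are some of the few pre-exacerbation observations that the design will yield, and so the precision of the TDS and SDI summaries.

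**Working it through.** **Inputs**
- From SAP 2.3: rates of 1.05 and 1.14 events per year (midpoint 1.095), 12 weeks of evaluation, 400 enrolled, 360 evaluable, 10% dropout, 91 expected events (73 to 110), probability above 0.99 of at least 70 events.
- From SAP 2.1: 100 patients per accelerometer subset.
- Assumed, because the documents are silent: the share f of patients with a short-memory device, the memory length, and that a full device stops recording.

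**Step 1. Reproduce the plan's figure.** 360 × 1.095 × 12/52 = 90.97, which matches 91. The Poisson 2.5% and 97.5% points at that mean are 73 and 110, and the probability of 70 or more is 0.990. The stated figures are reproduced.

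**Step 2. Events per subset.** 100 × 1.095 × 12/52 = 25.3 (24.2 to 26.3 over the two rates; Poisson 95% range 16 to 36). With 10% dropout, 90 × 1.095 × 12/52 = 22.7.

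**Step 3. Events removed by the rule.** Removed = events × f. The standard error grows by 1/√(1 − f).

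| f (assumed) | Removed of 25.3 | Removed of 22.7 | Standard error |
|---|---|---|---|
| 10% | 2.5 | 2.3 | +5% |
| 20% | 5.1 | 4.5 | +12% |
| 30% | 7.6 | 6.8 | +20% |

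**Step 4. How much could be recovered.** Assume that recording starts on Day 1 and stops at 6 weeks (Day 42), and that peaks fall evenly over 84 days. For a window of w days, an event is usable if days 1 to 7 are recorded, the window does not overlap them (peak day at least 8 + w), and the day before the peak is no later than Day 42 (peak day at most 43).
- w = 7: peak days 15 to 43, which is 29 days. 29/84 = 35%.
- w = 21: peak days 29 to 43, which is 15 days. 15/84 = 18%.

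The same count for longer memory:
- 8 weeks: 43/84 = 51% (7-day window) and 29/84 = 35% (21-day window).
- 10 weeks: 57/84 = 68% and 43/84 = 51%.

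At f = 20% and 6 weeks of memory, recovery is 5.05 × 29/84 = 1.7 events (7-day window) or 5.05 × 15/84 = 0.9 events (21-day window) per 100 patients.

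**Step 5. If a full device overwrites.** Accelerometers are read at the final visit (Protocol 6.1.4). A 6-week device read on Day 84 would then hold roughly Days 43 to 84. The baseline week and early events would be gone, and Step 4 would not apply.

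**The case against.** The strongest reply is that the rule may be harmless, or even useful. Four parts of it stand.

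- **The loss is not shown to have happened.** No passage says that any device lacked 12 weeks of memory. The schedule plans continuous collection from visit 2 to visit 5. A reader might infer that data were in fact discarded. The documents show only that the rule would discard them.
- **Some summaries do depend on recording length.** A reader might infer that no analysis needs a long recording. The maximum change from baseline (SAP 7.3.2.1, 7.4.2.1) does. Patients without an exacerbation have no stated cut-off, so early-ending recordings would pull their maximum toward smaller changes.
- **Loose entry could bring in poor baselines.** If a full device overwrites, days 1 to 7 are lost. The first-later-value rule could then set a baseline near or after the exacerbation. It therefore cannot be said that the restriction buys no protection against bias.
- **The outputs are descriptive.** SAP 7.3 and 7.4 plan no test of TDS or SDI. The predictive models are left to a separate report (SAP 7.5.3), and the SAP does not show whether the same restriction applies there.

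A further defence is that SAP 7 assigns all endpoint analyses to the ITT set, and that the pre-peak sections speak of a cohort rather than an analysis set. This wording should be reconciled, but it does not bring the patients back, because their TDS and SDI are never computed.

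None of this explains why the pre-peak and weekly tables should turn on capacity when SAP 4.6 already accepts short recordings from withdrawals.

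**Conclusion.** The point holds as a modest loss of precision in descriptive tables. For the pre-peak and weekly summaries, membership should follow the recorded days. As written, two patients with identical recordings are treated differently because of the device they wore.

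The size is conditional. The 2.3 to 2.5 events lost per 10% of patients excluded rest on the plan's own rates and on event risk being unrelated to device memory. The actual share of short-memory devices is unknown, and if it is zero the rule excludes nobody. The recoverable part (35% or 18% at 6 weeks) further assumes that recording stops when memory fills and that events are spread evenly.

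A reader might go further and conclude that about half of the lost events could be regained with 6 weeks of memory, since 42/84 = 0.5. That counts every event that occurs while the device records. It ignores the need for a baseline week and a separate pre-peak window. Nor do the documents support a claim that the rule biases the results, because capacity is on its face unrelated to outcome.

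**What to change.** A cheap improvement to SAP 3.4, 3.5, 7.3 and 7.4:

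1. Define each set by a successful download with at least one valid recorded day, whatever the device memory.
2. Admit a patient or event to each pre-peak, weekly-change or other change-from-baseline table only if a baseline from days 1 to 7 and the days that the table uses were actually recorded. Do not use the first-later-value baseline for short-memory devices.
3. Do not impute days lost to memory limits. The 7-day fill in SAP 4.6 should not extend past the end of a recording.
4. Keep the maximum-change summary on the 12-week-memory set, or take it over a common recording window.
5. State whether a full device stops or overwrites. Report the number of patients with short-memory devices and the contributing n per week.
6. Keep the 12-week-memory set as a secondary display.

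The cost is SAP wording, some extra programming, and reprocessing of files already downloaded. No new data are needed. The downside is that fewer patients contribute in later study weeks, which the weekly n will show.
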